#### **4.6.3.2. Vital Signs**

The number of participants with worst case vital sign results relative to potential clinical importance (PCI) criteria which are post-baseline relative to baseline will be summarised by test and category. The summary will include baseline data and worst case post-baseline, and planned visit. The baseline categories are: Low, within Range and High for PCI criteria. The change categories for PCI criteria are: To Low, To within Range or No Change, To High. The determination of worst case post-baseline takes into account both planned and unscheduled assessments. Changes in value from baseline for each vital sign will be summarized at every assessed time point. All vital sign data will be listed.

#### **4.6.3.3. ECG**

The number of participants with worst case QTc values relative to potential clinical importance criteria which are post-baseline relative to baseline will be summarised. The summary will include baseline data and worst case post-baseline, and visits (i.e. On-Therapy and TOC visits). The baseline categories are: Low, within Range and High for PCI criteria. The change categories for PCI criteria are: To Low, To within Range or No Change, To High. The determination of worst case post-baseline takes into account both planned and unscheduled assessments. A summary of change from baseline in ECG values will be produced by visit.

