1.3. Schedule of Activities (SoA)

Visit	Baseline		On-Therapy ^a	TOC ^b	Follow-up	Early Withdrawal	Notes
Study Day	1		2 to 4	10 to 13	28±3	NA	
Procedure	Pre-dose	Post-dose					
Written informed consent/assent	X						
IRT – Screening module	X						
Inclusion and exclusion criteria	X						
Participant demography	X						
Medical/surgical history	X						
IRT – Randomization module	X						
Randomization	X						
Schedule next visit	X		X	X	X		
 On Day 1, the planned return day/time for the On-therapy, TOC, and Follow-up Visits should be scheduled before the participant leaves the study site. Pre-visit reminder: Study site staff will contact the participant 24±4 hours before the scheduled On-therapy, TOC, and Follow-up Visits.
Assessments							
Physical examination (including height and weight at Baseline only)	X			X			At the TOC Visit, the physical examination may be symptom directed and is only required if indicated for a specific participant.
12-lead ECG	X	X	X	X			
 See Section 5.2 for ECG exclusion criterion for participants aged ≥12 to <18 years. For additional details see Section 7.1.2 and Section 8.2.3. For postdose on Day 1 and On-Therapy Visit, ECGs will be collected at approximately 2 hours postdose (i.e., expected time of maximum concentration; ECG collection should ideally be within approximately 1.5 hours postdose to 4 hours postdose). Electrocardiograms will be reviewed locally by the investigator for safety purposes.
Vital sign measurements	X		X	X			Take measurement of temperature, blood pressure, and pulse rate.
Record acute cystitis sign and symptoms	X		X	X	X	X	Individual clinical signs and symptoms scores of acute cystitis will be recorded by a study physician or otherwise appropriately medically trained staff based on participant interview and using the scoring system in 10.10. The same scorer will be used at all

Visit	Baseline		On-Therapy ^a	TOC ^b	Follow-up	Early Withdrawal	Notes
Study Day	1		2 to 4	10 to 13	28±3	NA	assessment time points for each participant, on all occasions, whenever possible.
Procedure	Pre-dose	Post-dose					

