2.3.1. Risk Assessment

Potential Risk of Clinical Significance	Summary of Data/Rationale for Risk	Mitigation Strategy
Gepotidacin (GSK2140944)		

Cardiovascular Effects Based on nonclinical data, cardiovascular effects were reversible increase in heart rate and blood pressure (dog and monkey); reversible 10 to 21 msec (4% to 9%) increase in QTc (monkey); and at the highest dose, a reversible 2 to 3 msec (6% to 8%) increase in QRS (monkey). Based on a thorough QTc clinical study, gepotidacin may cause mild, reversible heart rate effects and QT prolongation.
	
In a thorough QTc study, infusion of gepotidacin at doses of 1000 and 1800 mg over 2 hours caused a mild increased heart rate effect of approximately 6 to 10 bpm and QT prolongation measured as $\Delta\Delta QTcF$ of 12 to 22 msec. The QT prolongation evolved during the infusion and was quickly reversed over 2 hours after the end of the infusion (see the IB for details). In Phase I studies, concentration-dependent QT prolongation has been observed during clinical trials with gepotidacin; however, this increase has not translated into clinically significant QTc values or changes from baseline (change from baseline >60 msec or QTcF >500 msec) or cardiovascular AEs. In Phase I and II studies, gepotidacin did not have a clinically relevant effect on cardiac conduction (PR and QRS intervals). Although there appears to be a trend to higher gepotidacin systemic exposure in healthy Japanese compared to Western subjects, the higher systemic exposure of gepotidacin observed in Japanese subjects is currently considered to be within the tolerable range and not associated with any cardiovascular safety concerns.
	
See Section 5.2 for excluded cardiac conditions. Close monitoring of clinical parameters and AEs (Section 1.3) will be conducted, and treatment monitoring and evaluation criteria (Section 7.1.2) will be utilized to mitigate cardiovascular effects. Participants taking medications known to increase QT or potent CYP3A4 inhibitors will be excluded (see Section 6.8.2). See also the Renal and Hepatic sections within this table below.

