## 4. STATISTICAL ANALYSES

### 4.1. General Considerations

#### 4.1.1. General Methodology

Participants who prematurely withdrew from study will not be replaced.

In the case of wrong stratification assigned at the time of randomization, the analyses will be performed based on the actual stratum per data collected in the CRF.

Confidence intervals will use 95% confidence levels unless otherwise specified.

Unless otherwise specified, continuous data will be summarized using descriptive statistics: n, mean, standard deviation (std), median, minimum and maximum.

Categorical data will be summarized as the number and percentage of participants in each category.

It is anticipated that patient accrual will be spread thinly across centers and summaries of data by center would unlikely be informative and will not, therefore, be provided.

For any efficacy analyses of binary outcomes for which a risk difference will be estimated, if 100% (or 0%) success rates are observed in both treatment arms then a constant of 1E-10 will be added to each zero cell in the resultant contingency table to overcome software limitations and enable determination of the risk difference and two-sided 95% CI.

Out of stability (OOS) data may be delivered for microbiological urine samples. This data will not be included in any analysis, participants with OOS data will have their microbiological response missing and will be counted under the Unable to determine category.

Susceptibility interpretations will be based on CLSI M100 with the exception of nitroxoline and cefadroxil which are based on EUCAST guidelines and faropenem which is based on [Fuchs, 1995].

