### **Cardiovascular and Gastrointestinal AESIs**

The number and percentage of participants with an event will be summarized by PT, SOC and maximum grade. In addition, the incidence of AEs of GI effects and time to the first occurrence will be summarized.

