### 6.2.3. Criteria for Potential Clinical Importance

#### 6.2.3.1. ECG

ECG Parameter	Units	Potential Clinically Important Range	
		Lower	Upper
Absolute			
Absolute QTc Interval	msec	N/A	>450
Absolute PR Interval	msec	< 110	> 220
Absolute QRS Interval	msec	< 75	> 110

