## 6.2.7. Assessment Window

Unscheduled and withdrawal visit data will be slotted into a target visit based on visit window defined in the table below. If there are multiple assessments within the same window, the closest one to the target day will be taken in the slotting. If multiple records are equally close to the target day, then the later record will be utilized. For post-baseline records collected outside the analysis visit window, a blank analysis visit label will be assigned.

Analysis Set / Domain	Parameter (if applicable)	Target	Analysis Window		Analysis Timepoint
			Beginning Timepoint	Ending Timepoint	
All	All	Day 3	Day 2	Day 5	On-therapy
All	All	Day 12	Day 9	Day 16	Test-of-Cure
All	All	Day 28	Day 21	Day 31	Follow-up

The procedure of the analysis visit assignment is as follows.

1. Calculate the analysis days for planned visit, unscheduled visit, and early withdrawal visit with non-missing outcome if applicable. The calculation of the analysis days is provided in Section 6.2.6.
2. Slot the visits to each of analysis timepoint according to the above table.
  - a. If there are multiple assessments within the same windows, the closest one to the target day will be taken in the slotting.
  - b. If multiple records are equally close to the target day, then the later record will be utilized using the sequence number in SDTM dataset.
  - c. For post-baseline records collected outside the analysis visit window, a blank analysis visit label will be assigned. Such assessments will not be included in any of the by visit summaries. Descriptive summaries that are shown for “any assessment post baseline” e.g. maximum/minimum/ worst case post baseline, will use all assessments irrespective of whether they fall in an analysis visit window.

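### The SAP sets clinical-importance limits for PR and QRS but counts participants against the QTc limit only, so PR and QRS crossings without a reported adverse event go uncounted

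*SAP*

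**What the plan says.** SAP 6.2.3.1 tabulates limits of potential clinical importance for QTc, PR and QRS. The row labelled "Absolute PR Interval" has a lower and an upper limit, as does the QRS row. QTc has an upper limit only; its lower limit is N/A.

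SAP 4.6.3.3 then plans a shift-type summary of "The number of participants with worst case QTc values relative to potential clinical importance criteria", with Low, within-range and High categories at baseline and To Low, no-change and To High categories afterwards. It also plans change from baseline in ECG values by visit. Under SAP 4.1.1, "continuous data will be summarized using descriptive statistics: n, mean, standard deviation (std), median, minimum and maximum".

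The parallel paragraph for vital signs, SAP 4.6.3.2, is worded differently: results against the limits "will be summarised by test and category", and all vital sign data are listed.

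On timing, the Schedule of Activities (Protocol 1.3) says that on Day 1 post-dose and at the On-therapy Visit "ECGs will be collected at approximately 2 hours postdose (i.e., expected time of maximum concentration". SAP 6.2.7 starts its first analysis window at Day 2 and says of post-baseline records outside the windows: "Such assessments will not be included in any of the by visit summaries". Worst-case summaries, by contrast, use every post-baseline assessment whatever its window.

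**The concern.** A limit that no analysis uses does nothing. Followed as written, the SAP would not let the study report say how many women in each arm had a PR or QRS value beyond the sponsor's own limits, unless an investigator judged the change clinically significant and reported it as an adverse event. The by-visit statistics do not replace that count. The maximum change describes one woman, and since it is a change and not an absolute value, it does not show whether a limit was crossed.

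There is some reason to want the count. Protocol 2.3.1 reports a small reversible QRS increase in monkeys at the highest dose and names atrioventricular block among the more severe effects that increased cholinergic activity could bring. Protocol 4.3 reports a trend to 7% to 30% higher peak concentration in Japanese than in Western participants. The same risk section is also reassuring: in Phase I and II, "gepotidacin did not have a clinically relevant effect on cardiac conduction (PR and QRS intervals"), and no causal link between gepotidacin and events such as AV block has been established.

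**Working it through.** **1. Limits against outputs.** From SAP 6.2.3.1 and 4.6.3.3:

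| Interval | Lower limit (msec) | Upper limit (msec) | Worst-case count planned? |
|---|---|---|---|
| QTc | N/A | >450 | Yes |
| PR | <110 | >220 | No |
| QRS | <75 | >110 | No |

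Limits defined: 1 + 2 + 2 = 5. Limits used: 1. Unused: 5 − 1 = 4, which is two of the three parameters.

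**2. Categories.** Low and To Low need a lower limit. QTc has none, so in a QTc-only table these cells are always empty. Only PR and QRS could fill them. With the by-test wording for vital signs, this suggests that all three intervals were intended and that the wording is a drafting omission.

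**3. Other routes to the same information.**
- Change from baseline by visit gives distribution statistics, not counts of crossings.
- Protocol 8.2.3 makes an ECG change an adverse event only if it is clinically significant. Conduction terms such as AV block and bundle branch block are on the cardiovascular AESI list, for which "The number and percentage of participants with an event will be summarized by PT, SOC and maximum grade". This counts reported terms, not measured intervals.
- No other visible section counts PR or QRS values against a limit. The exploratory sections are redacted and cannot be checked, but the safety ECG section is fully visible.

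**4. The Day 1 post-dose ECG.** Planned post-baseline ECG time points in the Schedule of Activities are Day 1 post-dose, On-therapy and TOC: three in all, the first two near peak concentration. By SAP 6.2.6, study day = assessment date − reference date + 1. With dosing and assessment on the same date this is 0 + 1 = 1. The windows in 6.2.7 are Day 2 to 5, Day 9 to 16 and Day 21 to 31, and the slotting procedure covers planned visits. Day 1 falls in none of them. The record is not baseline either, since SAP 4.1.2 takes the latest pre-dose value. Read literally, it is left out of every by-visit summary. It enters the worst-case table, but that table covers QTc only. So for PR and QRS, one of three post-baseline time points, and one of the two near peak, reaches no summary.

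**5. What a count would support.** Planned gepotidacin enrolment is about 300 × 3/4 = 225. For illustration only:
- 0 of 225 crossing a limit: exact 95% upper limit = 1 − 0.025^(1/225) = 1.6%.
- 4 of 225: 4/225 = 1.8%, Clopper-Pearson 95% interval 0.5% to 4.5%.

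The planned PR and QRS outputs support neither kind of statement.

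**The case against.** The strongest reply is that no protocol analysis is missing. The secondary safety endpoint is change from baseline in ECGs, its summary measure is mean change, and Protocol 9.3.4 asks only for descriptive change. SAP 4.6.3.3 supplies this for ECG values in general, so any count against limits goes beyond the protocol. A QTc-only count could also be deliberate: QTc and QT are the only intervals with numeric eligibility or stopping limits, and QT prolongation is the only ECG finding named in the SAP's adverse-reaction screen. Investigators review the ECGs, so what stays uncounted is values beyond a limit that they did not consider clinically significant.

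All of that stands, and it keeps the point minor. It does not explain why the SAP defines PR and QRS limits and a Low category that nothing uses.

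On Day 1, one could argue that 6.2.7 opens by referring to unscheduled and withdrawal visits, has no baseline row, and so leaves Day 1 records to be handled elsewhere. But its stepwise procedure expressly includes planned visits, and the baseline rule takes only the pre-dose ECG, so no other rule in the visible text brings the post-dose record back in. That gap affects by-visit QTc change too; QTc, however, also has the worst-case table.

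It is also fair to say that 225 is planned enrolment. The Safety population excludes one site for a GCP violation, and enrolment runs until a microbiological target is met, so the actual number may differ.

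**Conclusion.** The concern holds as a minor safety-reporting gap. Four of the five ECG limits in SAP 6.2.3.1 feed no planned output, and PR and QRS from one of the two near-peak ECGs reach no summary. Measured PR or QRS crossings will be counted only if reported as adverse events.

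This rests on reading 4.6.3.3 and 6.2.7 as written; table shells, if they already include PR and QRS, are not among the documents. The protocol's mean-change ECG endpoint is met, a mean shift at On-therapy or TOC would be visible, and no efficacy result or stopping rule is affected. The 225-based intervals show what a count could say; they do not predict any event rate.

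**What to change.** In SAP 4.6.3.3, change the worst-case summary to cover QTc, PR and QRS values, by parameter and treatment group, using all post-baseline ECGs including Day 1 post-dose. State that Low and To Low apply to PR and QRS only.

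In SAP 6.2.7, add a Day 1 post-dose analysis time point for ECG, so that the by-visit change summary includes the first near-peak recording.

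The cost is SAP wording, two more blocks in an existing table and one row in the window table. The limits are already set and the ECGs already scheduled, so sites and participants have no extra work. If the table shells already cover PR and QRS, the SAP text should say so.

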#### **4.1.2. Baseline Definition**

For all endpoints the baseline value will be the latest pre-dose assessment with a non-missing value (or randomization date in participants who are randomized but did not receive study treatment), including those from unscheduled visits. If time is not collected, Day 1 Pre-dose assessments are assumed to be taken prior to first dose and used as baseline.

For clinical signs and symptoms assessments and microbiological assessments, all Day 1 symptom assessments and urine samples (collected for identification of uropathogens) are used as baseline regardless of if they were taken pre or post dose. Urine samples collected on Day -1 or Day 1 can be considered as baseline.

Unless otherwise stated, if baseline data is missing no derivation will be performed and baseline will be set to missing. If baseline data is missing, then change from baseline calculations will not be performed and will be set to missing.

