## 6.2.5. Study Period

Assessments and events will be classified according to the time of occurrence relative to the study intervention period.

**Pre-Intervention** is defined as time prior to the first dose of study intervention.

**On-Intervention** is defined as time from first dose to last date. If time of assessment or study intervention is not collected, the following assessment on the first dose date will be assumed to be taken prior to the first dose and therefore considered pre-intervention: ECG, Lab, and vital signs, and first dose date is considered on-intervention for AE and concomitant medication.

**Post-Intervention** is defined as any time post on-intervention window, i.e.  $>$  last dose date.

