## 6.2.6. Study Day and Reference Dates

The safety reference date is the study intervention start date (or randomization date if not dosed) and will be used to calculate study day for safety measures.

The efficacy reference date is the study intervention start date (or randomization date if not dosed) and will be used to calculate study day for efficacy measures and baseline characteristics, as well as efficacy durations.

The study day is calculated as below:

- Assessment Date = Missing → Study Day = Missing
- Assessment Date < Reference Date → Study Day = Assessment Date – Ref Date
- Assessment Date ≥ Reference Date → Study Day = Assessment Date – Ref Date + 1

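### The ECG scheduled about 2 hours after the first dose has no analysis visit, and the only QTc category (>450 msec) cannot show who met the protocol's stopping limits

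*SAP*

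**What the plan says.** **Protocol.** The Schedule of Activities (1.3) states: "For postdose on Day 1 and On-Therapy Visit, ECGs will be collected at approximately 2 hours postdose". It identifies this as the time when peak concentration is expected. Section 8 confirms that the Day 1 post-dose ECG is triplicate. Change from baseline in ECGs is a secondary safety endpoint (Section 3), its summary measure is the mean change (Table 1), and Section 9.3.4 plans descriptive summaries of that change over time. For adults, Section 7.1.2 sets limits for withdrawal from study intervention:

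- QTc >500 msec or uncorrected QT >600 msec
- QTc change from baseline >60 msec
- with bundle branch block, >500 msec if baseline QTc is <450 msec, and ≥530 msec if it is 450 to 480 msec

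**SAP.**

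- 4.1.2, baseline: "For all endpoints the baseline value will be the latest pre-dose assessment with a non-missing value".
- 6.2.6, study day: "Assessment Date ≥ Reference Date → Study Day = Assessment Date – Ref Date + 1".
- 6.2.7, windows for all domains: Day 2 to 5 (On-therapy), Day 9 to 16 (TOC) and Day 21 to 31 (Follow-up). "For post-baseline records collected outside the analysis visit window, a blank analysis visit label will be assigned". Such records are left out of by-visit summaries but kept in worst-case summaries.
- 4.6.3.3, QTc category table: "The summary will include baseline data and worst case post-baseline, and visits (i.e. On-Therapy and TOC visits". Change from baseline in ECG values is given by visit.
- 6.2.3.1: the row for "Absolute QTc Interval" has no lower limit and an upper limit of >450 msec. There is no change-from-baseline criterion.
- 6.2.5: where times are not collected, "the following assessment on the first dose date will be assumed to be taken prior to the first dose". ECG is among the assessments named.

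**The concern.** Protocol 2.3.1 reports concentration-dependent QT prolongation with gepotidacin. Protocol 4.3 reports a trend to a 7% to 30% higher peak plasma concentration in Japanese than in Western Caucasian participants. The QTc response at the first-dose peak in Japanese patients is thus something this trial is well placed to describe, and the protocol collects the ECG for it. If the SAP is programmed as written, no table shows the mean change at that time.

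The category table raises a second problem. Protocol 2.3.1 describes clinically significant QTc as a change >60 msec or QTcF >500 msec, and 7.1.2 uses the same two values for stopping. A table with a single cut at 450 msec cannot show how often either was reached.

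Other parts of the SAP do more. Vital signs (4.6.3.2) are summarised at every assessed time point and listed in full, and liver monitoring and stopping events (4.6.3.1) have their own summary.

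**Working it through.** The plan gives no figure to reproduce. The check passes each scheduled ECG through the SAP's rules, then classifies example QTc values.

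**1. Study day of the Day 1 post-dose ECG.** The assessment date equals the reference date, so study day = 0 + 1 = 1.

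**2. Window.** Day 1 lies in none of 2–5, 9–16 or 21–31. Baseline is the latest pre-dose value, so this ECG is a post-baseline record outside all windows and its label is blank.

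**3. Where each scheduled ECG appears.**

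| Scheduled ECG | Study day | Label | By-visit tables | Worst-case row |
|---|---|---|---|---|
| Day 1 pre-dose | 1 | Baseline | as baseline | no |
| Day 1, about 2 h post-dose | 1 | blank | **no** | yes |
| On-therapy, about 2 h post-dose | 2 to 4 | On-therapy | yes | yes |
| TOC | 10 to 13 | TOC | yes | yes |

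The TOC Visit is 5 to 8 days after treatment ends, so only two scheduled ECGs fall at an on-drug peak. One of those two has no by-visit result.

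**4. Number of participants.** Planned enrolment is about 300, randomised 3:1: 300 × 3/4 = 225 on gepotidacin and 75 on nitrofurantoin.

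**5. QTc categories.** The pairs below are assumed values chosen to illustrate the rules, not trial data.

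| Baseline → post-dose (msec) | Change | SAP category | >500 | >60 |
|---|---|---|---|---|
| 420 → 451 | 31 | To High | no | no |
| 440 → 510 | 70 | To High | yes | yes |
| 380 → 445 | 65 | within range / no change | no | yes |
| 470 → 535, bundle branch block | 65 | within range / no change | yes | yes |

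The first two rows share a category, although only the second passes a stopping limit. The third passes the change limit but looks unremarkable. This can happen for any baseline below 450 − 60 = 390 msec. The fourth is at or above the 530 msec limit for its baseline band, yet reads as no change because its baseline is already above 450 msec.

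**The case against.** **The Day 1 ECG is not lost.** This is correct. SAP 6.2.7 keeps out-of-window records in worst-case summaries, so a Day 1 QTc above 450 msec is captured, and the On-therapy peak ECG remains in the by-visit tables. But the worst-case row shows neither when the value occurred nor the mean change at that time.

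**The exclusion is partly inferred.** The restriction to On-Therapy and TOC is attached to the category table, while the change-from-baseline sentence says only that it is by visit. The opening of 6.2.7 mentions only unscheduled and withdrawal data. However, step 1 of the procedure in 6.2.7 also includes planned visits, and the blank-label rule covers all post-baseline records outside a window. Following the text gives no Day 1 post-dose row.

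**450 msec is a protocol limit.** It is, as the entry limit in exclusion criterion 22. What the table lacks is the stopping limits.

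**Participants who meet the stopping limits will appear elsewhere.** A reader might infer that they cannot be found at all. The documents do not support that. New clinically relevant ECG findings are to be reported as adverse events (Protocol 7.1.2). The SAP tabulates adverse events leading to discontinuation (4.6.2) and reasons for discontinuing (6.1.2), and it shortlists QT prolongation automatically (4.6.2.4). These outputs rest on reported events and decisions. They do not count measured QTc against the limits.

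**An untimed post-dose ECG could become the baseline.** A reader might infer this from SAP 6.2.5. The documents do not support it: baseline is governed by 4.1.2, which for untimed data uses the records labelled Day 1 pre-dose. Its exception for post-dose Day 1 data covers symptoms and urine samples, not ECGs. What stands is a mismatch: 6.2.5 treats any untimed ECG on the first dose date as pre-intervention, whatever its label. An untimed post-dose ECG might then also drop out of the worst-case row. This matters only if ECG times are missing, and nothing in the documents says that they will be.

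**Conclusion.** The point holds in two parts, both about descriptive safety reporting.

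First, the SAP as written gives no by-visit change or category result for one of the two scheduled on-drug peak-time ECGs. That falls short of the change over time planned in Protocol 9.3.4 for a secondary safety endpoint. The counts of about 225 and about 300 are planning figures. The Safety population will differ, because it requires at least one dose and excludes one site for a GCP violation.

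Second, the QTc category table can neither separate nor fully detect participants who met the Protocol 7.1.2 limits.

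No decision rule in the SAP depends on either table, and the primary analysis is unaffected. The conclusion rests on SAP 4.6.3.3, 6.2.3.1, 6.2.6 and 6.2.7, which can be read in full. SAP 4.4 and 4.5 are redacted, so nothing is inferred from them.

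**What to change.** 1. In SAP 6.2.7 and 4.6.3.3, add an ECG timepoint for Day 1 post-dose, assigned by the scheduled label, and include it in both the change-from-baseline and category summaries.
2. In the category table (SAP 4.6.3.3 and 6.2.3.1), add rows for the limits already in Protocol 7.1.2: QTc >500 msec, change >60 msec, uncorrected QT >600 msec, and the bundle branch block limits by baseline band. Apply them to the triplicate average, as 7.1.2 does, and label them as the adult limits.
3. Align SAP 6.2.5 with 4.1.2, so that an untimed Day 1 ECG is classed by its scheduled pre-dose or post-dose label.

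The cost is some SAP wording and extra rows in existing tables. No new data are needed, no limit is introduced or altered, and clinical management does not change.
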